## **Appendix 6 Dysgeusia treatment guidelines**

As there are no recognised standard international guidelines for the management of this multifactorial event, investigators are advised to consult their local practice guidelines for the management of dysgeusia. Please refer to Table 7 for instructions on dose reductions and interruptions for dysgeusia.

Some interventions may be effective in treating dysgeusia:

[figure not shown]
- Treatment with oral pilocarpine and artificial saliva may help in cases where there is also dry mouth
- Zinc supplements may help in cases where there is evidence of zinc deficiency
- Alpha lipoic acid is an antioxidant capsule supplement which may improve flavour sensation
- Good oral hygiene and chlorhexidine (or similar) mouthwashes

Patients may be advised of some ways that they can manage dysgeusia, for example:

- Cooking or eating food in non-metallic cookware
- Avoiding foods that taste bitter or metallic
- Flavoring foods with seasonings and spices
- Eating food cold may help to reduce unpleasant flavor sensations
- Frequently brushing teeth
- Rinsing with mouth wash regularly
- Using chewing gum. Lozenges or mints to stimulate saliva production

A dysgeusia treatment algorithm has been developed by Sevryugin et al. {Sevryugin, 2021 Ref 36} based on their review of published studies of dysgeusia interventions and is included to assist Investigators with the management of dysgeusia that occurs during treatment with RXC004. However, it is acknowledged that not all of the management suggestions may be readily available or applicable to patients in this study.

Figure from {Sevryugin, 2021 Ref 36}

**Legend:**  
 PO: by mouth; TID: three times a day; BID: twice a day; QID: four times a day

## Appendix 7 Prohibited CYP3A4 Inhibitors and Inducers

CYP 3A4 Inhibitors	CYP 3A4 Inducers

Strong CYP 3A4 Inhibitors
 
Concomitant use of these drugs has the potential to increase the exposure of RXC004 over 5-fold            These agents must not be given within 14 days of first dose of study treatment
 
boceprevir, cobicistat, danoprevir and ritonavir, elvitegravir and ritonavir, grapefruit juice, indinavir and ritonavir, itraconazole, ketoconazole, lopinavir and ritonavir, paritaprevir and ritonavir and (ombitasvir and/or dasabuvir), posaconazole, ritonavir, saquinavir and ritonavir, telaprevir, tipranavir and ritonavir, troleandomycin, voriconazole, clarithromycin, idelalisib, nefazodone, nelfinavir,
	
Strong CYP 3A4 Inducers
 
Concomitant use of these drugs has the potential to decrease the exposure of RXC004 by over 80%            These agents must not be given within 14 days of first dose of study treatment
 
apalutimide, carbamazepine, enzalutamide, mitotane, phenytoin, rifampin, St. John's wort

Moderate CYP3A4 Inhibitors
 
Concomitant use of these drugs has the potential to increase the exposure of RXC004 by 2-5-fold            A washout period of 14 days is recommended and a minimum washout period of 5 half-lives (See SMPC or USPI) is required before first dose of study treatment.
 
aprepitant, ciprofloxacin, conivaptan, crizotinib, cyclosporine, diltiazem, dronedarone, erythromycin, fluconazole, fluvoxamine, imatinib, tofisopam, verapamil lansoprazole
	
Moderate CYP 3A4 Inducers
 
Concomitant use of these drugs has the potential to decrease the exposure of RXC004 by 60-80%            A washout period of 14 days is recommended and a minimum washout period of 5 half-lives (See SMPC or USPI) is required before first dose of study treatment.
 
bosentan, efavirenz, etravirine, phenobarbital, primidone


Weak CYP3A4 Inhibitors
 
These are not prohibited but should be used with caution as they may increase the exposure of RXC004 by 1.25 -2- fold
 
chlorzoxazone, cilostazol, cimetidine, clotrimazole, fosaprepitant, istradefylline, ivacaftor, lomitapide, ranitidine, ranolazine, ticagrelor, omeprazole
	
Weak CYP3A4 Inducers
 
These drugs are not prohibited- they have the potential to decrease the exposure of RXC004 by 20-50% which is within the scope of the dose reduction allowances
 
armodafinil, modafinil, rufinamide

For updated information, please refer to <https://www.fda.gov/drugs/drug-interactions-labeling/drug-development-and-drug-interactions-table-substrates-inhibitors-and-inducers>

## Appendix 8 Nivolumab Toxicity Management and Dose Modification Guidelines (Patients enrolled onto Module 2 only)

Recommendations for nivolumab modifications are provided in the dose-modification section of the nivolumab Prescribing Information and summarised here.

### Nivolumab toxicity management and dose modifications

Adverse Event	Severity	Investigations, Treatment and Dose modification
Colitis	Grade 1 diarrhoea or colitis	
Investigations: FBC, UEC, LFTs, CRP, TFTs. Stool microscopy for leucocytes/ova/parasites, culture, viral PCR, C. diff. toxin and cryptosporidia
 
Treat with oral fluids and loperamide. Avoid high fibre/lactose diet. If Grade 1 symptoms persist for >14 days treat as per Grade 2
 
Continue treatment

	Grade 2 diarrhoea or colitis	
Investigations as per Grade 1. Exclude steatorrhea
 
Consider abdominal X-ray and sigmoidoscopy/colonoscopy for signs of Colitis.
 
Start prednisolone 0.5-1mg/kg or consider oral budesonide 9mg od if no bloody diarrhoea. Once recovered to Grade 1, wean steroids over 2-4 weeks. If no improvement in 72hrs, treat as per Grade 3.
 
Withhold dosea

	Grade 3 diarrhoea or colitis	
Investigations as per Grade 2 with daily FBC, UEC, LFTs and CRP
 
Conduct Sigmoidoscopy/colonoscopy and consider biopsy. Early surgical review if bleeding, pain or distension. Review diet (e.g nil by mouth, clear fluids, TPN)
 
Treat with IV (methyl)prednisolone 1-2 mg/kg. Wean steroids over 4-8 weeks. If no improvement in 72 hours start Infliximab 5mg/kg (if no perforation/sepsis/TB/hepatitis/congestive heart failure – Must have had flexsigmoidoscopy/colonoscopy prior)b
 
Withhold dosea

Adverse Event	Severity	Investigations, Treatment and Dose modification
	Grade 4 diarrhoea or colitis	Investigations and treatment as per Grade 3  Permanently discontinue
Pneumonitis	Grade 1	Bloods (FBC/UEC/LFTs/Ca/ESR/CRP). Consider sputum sample screening for viral/bacterial infection.  Chest X-ray  Continue treatment
	Grade 2	Investigations as per Grade 1. Monitor symptoms daily  Start antibiotics if suspicion of infection. If no evidence of infection or no improvement with antibiotics after 48hrs add in prednisolone 1mg/kg/day orally. Once improved to baseline, wean steroids over at least 6 weeks. If no improvement after 48hrs, manage as per Grade 3  Consider Pneumocystis prophylaxis depending on the clinical context  High resolution CT +/- bronchoscopy and BAL pending appearances  Withhold dose a
	Grade 3 or 4	Admit patient and perform investigations as per Grade 2.  Treat with (methyl)prednisolone IV 2-4 mg/kg/day and cover with empiric antibiotics. Once improved to baseline wean steroids over at least 8 weeks. If no improvement after 48hrs add infliximab 5mg/kg (or MMF if concurrent hepatic toxicity).  High resolution CT +/- bronchoscopy and BAL pending appearances  Permanently discontinue
Hepatitis (non-HCC)	Grade 1: ALT or AST >ULN-3XULN	If > ULN-3XULN repeat in 1 week  Continue treatment

Adverse Event	Severity	Investigations, Treatment and Dose modification
	
Grade 2:            ALT or AST 3-5XULN
	
Re-check LFTs/INR/albumin every 3 days. Review medications, e.g. statins, antibiotics and alcohol history. Perform liver screen: Hepatitis A/B/C serology, Hepatitis E PCR, anti-ANA/SMA/LKM/SLA/LP/LCI, iron studies
 
If rising ALT/AST when re-checked start oral prednisolone 1 mg/kg. Once resolved to Grade 1, wean steroids over 2 weeks. Re-escalate if worsening; Nivolumab treatment may be resumed once prednisolone <math>\leq</math> 10 mg
 
Consider imaging for metastases/clot
 
Withhold dosea

	
Grade 3:AST or ALT 5-20XULN
	
Re-check LFTs/INR/albumin every day. Other investigation as per Grade 2.
 
If ALT/AST < 400 and normal bilirubin/INR/albumin treat with oral prednisolone 1 mg/kg. If ALT/AST > 400 or raised bilirubin/INR/low albumin treat with i.v. (methyl)prednisolone 2 mg/kg. Once improved to G2, can change to oral prednisolone and wean over 4 weeks
 
Perform US with Doppler. Low threshold to admit if clinical concern
 
Permanently discontinue

	
Grade 4: ALT or AST >20xULN
	
Investigations as per Grade 3
 
Treat with i.v. (methyl)prednisolone 2 mg/kg. If condition worsens despite steroids, add mycophenolate mofetil (MMF) 500-1000 mg bd. If worse on MMF, consider addition of tacrolimus.
 
Hepatology consult and consider liver biopsy
 
Permanently discontinue

Hepatitis (HCC)
	
ALT/AST within normal limits at baseline and increases to >3-5XULN            Or
	
Re-check LFTs/INR/albumin every 1-3 days
 
If rising ALT/AST when re-checked start oral prednisolone 1 mg/kg. If no improvement within 3-5 days on oral prednisolone 1 mg/kg, consider additional workup (liver biopsy, liver US) and

Adverse Event	Severity	Investigations, Treatment and Dose modification
	AST/ALT is more than 1-3XULN at baseline and increases to 5-10XULN	
treatment with methylprednisolone 2-4mg/kg/day. Immunosuppressives (e.g.MMF) should be considered if no improvement on steroids.
 
If toxicity resolves to Grade <math>\leq</math>1 or baseline, wean steroids over 2 weeks. Re-escalate if worsening; nivolumab treatment may be resumed once prednisolone <math>\leq</math> 10 mg.
 
Consider hepatologist consult and US with Doppler
 
Withhold dosea

	AST/ALT increased to >10XULN or total bilirubin increases to >3XULN	
Investigations and treatment as above.
 
Permanently discontinue

Hypophysitis	Grade 2	
Pituitary axis assessment, MRI pituitary protocol (also exclude brain metastases), visual field assessment. Monitor TFTs.
 
Start oral prednisolone 0.5-1 mg/kg od after pituitary axis assessment. If no improvement in 48h, treat as severe with i.v. (methyl)prednisolone. Wean steroids based on symptoms over 2-4 weeks to 5 mg prednisolone. Do not stop steroids
 
Refer to or consult endocrinologist
 
Withhold dosea

	Grade 3	
Investigations as per Grade 2
 
Initiate i.v. (methyl)prednisolone 1 mg/kg after sending bloods for pituitary axis assessment. Analgesia as needed for headache. Aim convert to prednisolone and wean as symptoms allow over 4 weeks to 5 mg
 
Refer to or consult endocrinologist
 
Withhold dosea

	Grade 4	
Investigations as per Grade 1
 
Treatment as per Grade 3
 
Refer to or consult endocrinologist

Adverse Event	Severity	Investigations, Treatment and Dose modification
		Permanently discontinue
Adrenal Insufficiency	Grade 2	Withhold dose a
	Grade 3 or 4	Permanently discontinue
Type 1 Diabetes Mellitus	Grade 3 hyperglycemia	Admit to hospital immediately and start treatment of newly onset type I DM.  Withhold dose a
	Grade 4 hyperglycemia	Treat as per Grade 3  Permanently discontinue
Nephritis and Renal Dysfunction	Grade 1 (creatinine 1.5 x baseline or > ULN-1.5x ULN)	Review hydration status, medications, urine test/culture if urinary tract infection symptoms Dipstick urine and send for protein assessment UPCR. Repeat creatinine weekly. If worsens, manage as per Grade 2  If obstruction suspected: renal ultrasound +/- doppler to exclude obstruction/clot  Continue treatment
	Grade 2: creatinine > 1.5-3x baseline or > 1.5-3x ULN	Investigation as per Grade 1 and review creatinine/K+ in 48h-72h; if not improving discuss with nephrologist and need for biopsy and if attributed to irAE, If proteinuria: for 24 h collection or UPCR  If blood: phase contrast microscopy and GN screen* if nephrologist recommends  Initiate steroids (oral prednisolone 0.5-1 mg/kg)  Renal ultrasound +/- doppler to exclude obstruction/clot  Withhold dose a - Repeat creatinine/K+ every 48h If returns to Grade 1/baseline – recommence treatment (if on steroids, only once < 10 mg prednisolone)  If not attributed to irAE - may continue treatment
	Grade 3: creatinine > 3x baseline or > 3-6x ULN Serum creatinine more than 1.5 and up to 6 times the ULN	Investigation per Grade 2, plus admit patient for monitoring and fluid balance; repeat creatinine every 24 h; early discussion with nephrologist and need for biopsy; if worsening, initiate (methyl)prednisolone 1-2 mg/kg i.v.

Adverse Event	Severity	Investigations, Treatment and Dose modification
		Withhold dose a
	Serum creatinine >6 x ULN	Investigations per Grade 3, plus patient should be managed in hospital where renal replacement therapy is available  initiate i.v.(methyl)prednisolone 1-2 mg/kg  Permanently discontinue
Skin	Grade 1 (skin rash with or without symptoms, <10% BSA)	Physical examination. Exclude other causes e.g. viral illness, infection, other drug rash etc.  Topical steroids (mild strength) +/- oral or topical anti-histamines may be administered  Continue treatment
	Grade 2 (10-30% BSA)	Investigations as per Grade 1  Topical steroids (moderate strength) +/- oral or topical anti-histamines may be administered  Consider dermatology referral and skin biopsy  Continue treatment
	Grade 3 rash (>30% BSA, or 10-30% BSA with substantial symptoms) or suspected Stevens-Johnson syndrome (SJS) or toxic epidermal necrolysis (TEN)	Investigations as per Grade 1  Topical treatments as above (potent). Initiate steroids: if mild to moderate 0.5-1 mg/kg prednisolone od for 3 days then wean over 1-2 weeks; or if severe i.v. (methyl)prednisolone 0.5 -1 mg/kg and convert to oral steroids on response, wean over 2-4 weeks  Dermatology referral and skin biopsy  Withhold dose a
	Grade 4 rash or confirmed SJS or TEN	Investigations as per Grade 1  i.v. (methyl)prednisolone 1-2 mg/kg  Seek urgent dermatology review  Permanently discontinue

Adverse Event	Severity	Investigations, Treatment and Dose modification
Peripheral neurological toxicity (For specific recommendations for Myasthenia Gravis and Guillain-Barré syndrome, see 'other')	Grade 1	
Comprehensive neurological examination Diabetic screen, B12/folate, HIV, TSH, consider vasculitic & autoimmune screen, review alcohol history & other medications
 
Consider need for MRI/MRA brain or spine (exclude CVA, structural cause)
 
Continue treatment

	Grade 2	
Investigations as per Grade 1, plus consider NCS/EMG for lower motor neurone motor and/or sensory change
 
Consider pulmonary function/sniff/diaphragmatic function tests and neurological consultation
 
Initial observation reasonable or initiate prednisolone 0.5-1 mg/kg (if progressing, e.g. from mild) and/or pregabalin or duloxetine for pain. Taper steroids over 4-8 weeks. If worsening, treat as per Grade 3
 
Withhold dosea

	Grade 3	
Admit patient. Involve neurologist in care. Daily neurological review +/- daily vital capacity
 
MRI brain/spine advised NCS/EMG. Lumbar puncture. Pulmonary function assessment
 
Initiate (methyl)prednisolone 2 mg/kg i.v. Taper steroids over 4-8 weeks.
 
Withhold dosea

Encephalitis	New-onset moderate or severe neurologic signs or symptoms	
Lumbar puncture, PCR for HSV, cytology and consider viral culture
 
Oral prednisolone 0.5-1 mg/kg or i.v. (methyl)prednisolone 1-2 mg/kg if very unwell (Exclude bacterial and ideally viral infections prior to high-dose steroids). Consider concurrent empiric antiviral (i.v. acyclovir) and antibacterial therapy
 
CNS imaging and consider neurological consultation

Adverse Event	Severity	Investigations, Treatment and Dose modification
		Withhold dose a
	Immune-mediated encephalitis	
Lumbar puncture, PCR for HSV, cytology and consider viral culture
 
Oral prednisolone 0.5-1 mg/kg or i.v. (methyl)prednisolone 1-2 mg/kg if very unwell (Exclude bacterial and ideally viral infections prior to high-dose steroids). Consider concurrent empiric antiviral (i.v. acyclovir) and antibacterial therapy
 
CNS imaging
 
Permanently discontinue

Thyroid function	Hypothyroidism: Low FT4 with elevated TSH or TSH > 10 with normal FT4	
Thyroxine 0.5-1.5 µg/kg (start low in elderly, if cardiac history)
 
Continue treatment

	Thyrotoxicosis (DDx thyroiditis, Grave's disease)	
Investigations: Anti-TSH Receptor Ab, anti-TPO Ab, nuclear medicine thyroid uptake scan
 
Propranolol or atenolol for symptoms; consider carbimazole if anti-TSH Receptor Ab positive          Painful thyroiditis – consider prednisolone 0.5 mg/kg and taper if unwell,
 
Withhold dosea

Infusion reactions	Grade 1 or 2	Interrupt or slow rate of infusion
	Grade 3 or 4	Permanently discontinue
Other	Other Grade 3 AEs - First occurrence - Recurrence of same Grade 3 adverse events	
Withhold dosea
 
Permanently discontinue

	Life-threatening or Grade 4 adverse reaction	Permanently discontinue
	Grade 3 myocarditis	
If myocarditis is suspected, admit the patient and immediately start high-dose (methyl)prednisone (1–2mg/kg). In the case of deterioration, consider adding another immunosuppressive drug (MMF or tacrolimus)
 
Permanently discontinue

	Guillain-Barré syndrome (GBS)	
Nerve conduction studies (acute polyneuropathy)
 
Lumbar puncture (elevated protein with normal WBC count). Pulmonary function tests with vital

Adverse Event	Severity	Investigations, Treatment and Dose modification
		
capacity and maximum inspiratory/expiratory pressures. Antibody testing for GBS variants, e.g. GQ1b in Miller Fisher variant
 
Use of steroids not recommended in idiopathic GBS            If no improvement or worsening, plasmapheresis or intravenous immunoglobulin indicated.
 
Neurological consultation. Consider location of care where ventilatory support available (required in 15%-30% idiopathic cases)
 
Permanently discontinue

	Myasthenia Gravis	
Check for ocular muscle and proximal muscle fatigability. AChR and anti-MuSK antibodies
 
Bedside tests, e.g. Tensilon test or ice pack test with neurological input. Repetitive nerve stimulation and single fibre EMG
 
Steroids indicated (oral or i.v. depending on symptoms). Pyridostigmine initial dose 30 mg tds. If no improvement or worsening, plasmapheresis or IVIG may be considered
 
Additional immunosuppressants azathioprine, cyclosporine, mycophenolate
 
Avoid certain medications, e.g. ciprofloxacin, beta-blockers, that may precipitate cholinergic crisis
 
Neurological consultation
 
Permanently discontinue

	Requirement for 10mg per day or greater prednisone or equivalent for more than 12 weeks	Permanently discontinue
	Persistent Grade 2 or 3 adverse event lasting 12 weeks or longer	Permanently discontinue

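### Appendix 8 prints a second Grade 3 nephritis criterion (>1.5 to 6 x ULN) that takes in the whole Grade 2 ULN band, so admission and the option to continue nivolumab are ambiguous in Module 2

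*Protocol*

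**What the plan says.** Protocol Appendix 8 (Nephritis and Renal Dysfunction) sets out the creatinine rows as follows.

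- Grade 1: "Grade 1 (creatinine 1.5 x baseline or > ULN-1.5x ULN". Nivolumab continues.
- Grade 2: "Grade 2: creatinine > 1.5-3x baseline or > 1.5-3x ULN". The site is to "review creatinine/K+ in 48h-72h" and start oral steroids. Nivolumab is withheld, with one exception: "If not attributed to irAE - may continue treatment".
- Grade 3, first line of the cell: "Grade 3: creatinine > 3x baseline or > 3-6x ULN".
- Grade 3, second line of the same cell: "Serum creatinine more than 1.5 and up to 6 times the ULN". The action is investigation as for Grade 2, "plus admit patient for monitoring and fluid balance", daily creatinine and i.v. steroid if the patient worsens. Nivolumab is withheld.
- Last row, with no grade label: "Serum creatinine >6 x ULN". Nivolumab is permanently discontinued.

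Sites are sent to this table from two places. Section 5.3.7 refers nivolumab-related adverse events to Appendix 8, and Table 6 refers any event that meets a nivolumab hold. Section 2.1.1, criterion 8, allows entry with serum creatinine up to 1.5 x ULN, and section 5.3.2.1 applies the core criteria to Module 2.

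**The concern.** The two lines of the Grade 3 cell cannot both define Grade 3. The second starts at the lower limit of Grade 2, so a creatinine that the table labels Grade 2 also satisfies the Grade 3 cell.

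Two instructions then differ for the same value. Grade 2 is a review at 48 to 72 hours, and Grade 3 is an admission. Grade 2 lets nivolumab go on when the rise is not immune-related, and Grade 3 is silent on that. Two sites could follow the table faithfully and treat the same patient differently.

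The other differences between the rows are not part of the point. The default hold is the same in both, daily creatinine checks also satisfy the Grade 2 repeat interval, and the i.v. steroid applies only on worsening and can be read as escalation.

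**Working it through.** **Inputs.** All bands come from the nephritis rows of Appendix 8. The entry limit of 1.5 x ULN comes from section 2.1.1. Baselines of 0.8, 1.0 and 1.4 x ULN are assumed for illustration; all three are within the entry limit.

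**Step 1: the bands on the ULN scale without the second line.** Grade 1 is (1, 1.5], Grade 2 is (1.5, 3], Grade 3 is (3, 6] and discontinuation is above 6. They are contiguous and do not overlap.

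**Step 2: add the second line, (1.5, 6].**

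- It equals the Grade 2 and Grade 3 bands joined: (1.5, 3] plus (3, 6]. It covers nothing new.
- Its overlap with Grade 2 is (1.5, 3], a length of 3 - 1.5 = 1.5 out of 1.5, or 100%.
- The first Grade 3 line has no overlap with Grade 2 on this scale.
- Test values of 1.6, 2, 2.5 and 3 x ULN each meet both rows. Values of 3.1 and 6 meet Grade 3 only.
- A value that is >1.5 to 3 x baseline but not above 1.5 x ULN is not caught by the second line.

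**Step 3: the rise from baseline at which the Grade 3 cell is first met.** For a baseline of b x ULN, the fold-rise is min(1.5, 3b)/b with the line and min(3, 3b)/b without it.

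| Baseline b (x ULN) | With the line | Without the line |
|---|---|---|
| 0.8 | 1.5/0.8 = 1.88 | 2.4/0.8 = 3.00 |
| 1.0 | 1.5/1.0 = 1.50 | 3/1.0 = 3.00 |
| 1.4 | 1.5/1.4 = 1.07 | 3/1.4 = 2.14 |

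The last row needs care. A 1.07-fold rise from 1.4 x ULN already enters Grade 2, with its default hold, whether or not the line is there. What the line changes is whether the patient also falls under the admission instruction.

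**Step 4: what remains after the line is deleted.** The criterion of more than 3 x baseline stays in the Grade 3 cell. For b below 1, 3b is below 3, so it still reaches into Grade 2. At b = 0.8, 3b = 2.4, and values in (2.4, 3] x ULN meet both rows. That is 0.6/1.5 = 40% of the Grade 2 ULN band. At b = 1.0 or above, 3b is at least 3 and this overlap is empty.

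**The case against.** The strongest objection is that the table is damaged rather than wrong. The line has the same ungraded form as the discontinuation row below it and reads like a hold threshold for Grades 2 and 3 together. It also sits next to a page break, so it could be a separate hold-only row whose border was lost when the text was taken from PDF. That cannot be excluded, but three things make it unlikely.

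- The line comes before the break and has no action of its own.
- The hold instruction that follows the repeated table header has an empty severity cell. The same continuation pattern occurs for Grade 4 hypophysitis and for encephalitis, where the action clearly belongs to the row above.
- If that hold belonged to a separate row, Grade 3 nephritis would have no dose action at all, unlike the other graded nephritis rows.

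Even as a separate row, an unconditional hold over >1.5 to 6 x ULN would conflict with the Grade 2 exception. Only the admission difference would disappear.

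A second objection is that a precedence rule may exist. The table carries markers a, b and *, and their text does not appear in the available protocol text. The grade labels also point a sensible reader to Grade 2 at 2 x ULN. This stands as a limit: the claim is only that the visible text gives no rule.

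A third objection is that deletion does not fully separate the rows. This is correct (Step 4), and the fix allows for it.

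A reader might also infer that 2 x ULN becomes a Grade 3 DLT. The documents do not support that. Section 5.3.6 defines non-haematological DLTs by CTCAE grade, and section 7.2.1 grades events by CTCAE version 5.0, not by this table.

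**Conclusion.** The point holds as a minor inconsistency in an operative patient-care table, in Module 2 only (about 18 patients planned, Protocol section 9.1). As printed, every value in >1.5 to 3 x ULN meets both the Grade 2 and the Grade 3 row. The consequence is limited to inconsistent admission and inconsistent use of the option to continue nivolumab. The second is the narrower, because section 5.3.7 covers only nivolumab-related events, while Table 6 is wider.

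A reader might infer that the hold threshold is wrong or that patients would be under-treated. Neither follows: both rows withhold by default, and the ambiguity leans towards closer monitoring. A reader might also infer biased safety results, since section 4.1 makes inpatient hospitalisation a criterion for seriousness. Differing admissions could affect how single events are reported, but no planned analysis changes and the documents do not say how many patients reach this range, so no size can be put on it.

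The conclusion assumes that the line belongs to the Grade 3 cell, as the text shows, and that the missing footnotes contain no precedence rule.

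**What to change.** 1. Check the source table, its footnotes and the nivolumab Prescribing Information that Appendix 8 summarises.
2. Delete the second line, so that Grade 3 is >3 x baseline or >3 to 6 x ULN. No hold coverage is lost, because the Grade 2 and Grade 3 rows together already withhold over >1.5 to 6 x ULN. If the line was meant as a hold threshold, move it to a dose-hold note that covers Grades 2 and 3 and keeps the Grade 2 exception for rises that are not immune-related.
3. Add one sentence: if both rows are met, the higher grade applies. The row above 6 x ULN should be named as the highest, since it has no grade label. For a baseline within the entry limit, 3 x 1.5 = 4.5 is below 6, so any value above 6 x ULN also meets the Grade 3 baseline criterion.

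Steps 2 and 3 belong together. With the line left in place, a higher-grade rule would send every patient in >1.5 to 3 x ULN to admission.

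The cost is one line and one sentence at the next amendment. No extra data are needed.
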